11. SAFETY ANALYSES

11.1. Concomitant Medications

Concomitant medications are defined as any medication that started prior to treatment initiation and is ongoing during treatment, or any medication that starts after the initiation of treatment. These will be coded to Anatomical Therapeutic Classification (ATC) and by the preferred medication names using WHO-Drug dictionary (WHODrug Mar-15). Incidence of participants taking concomitant medications will be summarized by treatment group.

11.2. Adverse Events

All treatment emergent Adverse events (TEAEs) will be recorded and classified on the basis of Medical Dictionary for Regulatory Activities (MedDRA) terminology (Version 20.0). TEAEs will be defined as AEs reported after the first treamtment into the study.

TEAEs will be summarized by the number of participants reporting a TEAE, SOC, preferred term, severity, relationship to treatment (causality), and seriousness. When summarizing AEs by severity and relationship, each participant will be counted only once, within a system organ class or a preferred term, by using the event with the highest severity and greatest relationship within each classification.

[figure not shown]

In addition, a summary table of participants who prematurely discontinue treatment due to an AE will be provided.

12. **REPORTING CONVENTIONS**

Reporting conventions will adhere when possible to the International Conference on Harmonization (ICH) Guidance document E3, "Structure and Content of Clinical Study Reports". Some specific conventions are outlined below:

- 1. All tables and listings will be in landscape format.
- 2. All SAS output for tables and listings will be distributed in PDF files.

LIST OF TABLES

Table Number	Title	Population Summarized
14.1.1	Summary of Participants Disposition	(All Participants)
14.1.2	Demographics	(ITT Population)
14.1.3	Family History of Hair Loss	(ITT Population)
14.1.4	General Medical and Surgery History	(ITT Population)
14.2.1.1	Hair Counts at Week 16	(ITT Population)
14.2.1.2	Hair Counts at Week 16	(PP Population)
14.2.2.1	Hair Counts at Week 8	(ITT Population)
14.2.2.2	Hair Counts at Week 8	(PP Population)
14.2.3.1	Hair Counts at Week 26	(ITT Population)
14.2.3.2	Hair Counts at Week 26	(PP Population)
14.2.4.1	SECONDARY EFFICACY - Independent Physician Global Assessment	(ITT Population)
14.2.4.2	SECONDARY EFFICACY - Independent Physician Global Assessment	(PP Population)
14.2.5.1	SECONDARY EFFICACY - Investigative Site Physician Global Assessment	(ITT Population)
14.2.5.2	SECONDARY EFFICACY - Investigative Site Physician Global Assessment	(PP Population)
14.2.6.1	SECONDARY EFFICACY – Subjective Scalp Hair Growth Score at Week 8	(ITT Population)
14.2.6.2	SECONDARY EFFICACY – Subjective Scalp Hair Growth Score at Week 8	(PP Population)
14.2.7.1	SECONDARY EFFICACY – Subjective Scalp Hair Growth Score at Week 16	(ITT Population)
14.2.7.2	SECONDARY EFFICACY – Subjective Scalp Hair Growth Score at Week 16	(PP Population)
14.2.8.1	SECONDARY EFFICACY – Subjective Scalp Hair Growth Score at Week 26	(ITT Population)
14.2.8.2	SECONDARY EFFICACY – Subjective Scalp Hair Growth Score at Week 26	(PP Population)
14.2.9.1	SECONDARY EFFICACY – Hair Specific Skindex-29 QOL At Week 8	(ITT Population)
14.2.9.2	SECONDARY EFFICACY – Hair Specific Skindex-29 QOL At Week 8	(PP Population)
14.2.10.1	SECONDARY EFFICACY – Hair Specific Skindex-29 QOL At Week 16	(ITT Population)
14.2.10.2	SECONDARY EFFICACY – Hair Specific Skindex-29 QOL At Week 16	(PP Population)
14.2.11.1	SECONDARY EFFICACY – Hair Specific Skindex-29 QOL At Week 26	(ITT Population)
14.2.11.2	SECONDARY EFFICACY – Hair Specific Skindex-29 QOL At Week 26	(PP Population)
14.3.1.1	Overall Summary of Treatment Emergent Adverse Events	(SAF Population)
14.3.1.2	Summary of Treatment Emergent Adverse Events by System Organ Class(SOC)	(SAF Population)
14.3.1.3	Summary of Treatment Emergent Adverse Events by System Organ Class(SOC)and Severity	(SAF Population)
14.3.1.4	Summary of Treatment Emergent Adverse Events by System Organ Class(SOC)and Relatedness	(SAF Population)

Table Number	Title	Population Summarized
14.3.1.5	Summary of Serious Treatment Emergent Adverse Events	(SAF Population)
14.3.1.6	Summary of Treatment Emergent Adverse Events Resulting in Discontinuation	(SAF Population)
14.3.2	Concomitant Medications	(SAF Population)
14.3.3	Physical Examination Findings	(SAF Population)
14.4	Device Issues at Disposition	(ITT Population)
14.5	Treatment Compliance	(ITT Population)

LIST OF LISTINGS

Lising Number	Title	Population Summarized
1.1.1	Major Protocol Deviation	(SAF Participants)

2019-11

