2.5 Study Population and Source of Participants

All participants with diagnosis of androgenic alopecia may be eligible for study participation. Potential study candidates will be approached for consent prior to any data collection. A screening and enrollment log will be provided to study sites to maintain a record of all screened participants.

Participants will be identified and recruited by Clinical Investigators and/or their designated research staff at facilities affiliated with a maximum of 4 investigative sites. Clinical Investigators selected to participate in the study should be able to enroll at least 10 participants per month with a maximum of 100 participants enrolled at a single site.

For the purposes of enrollment, only those participants who meet all eligibility criteria, sign an IRB/HREC approved consent form and begin treatment with REVIAN/SHAM will be considered enrolled in the study. Participants who consent to participate but withdraw prior to the first treatment with REVIAN/SHAM will be considered a screening failure and the reasons for screening failure will be documented on the site screening log. All treated participants will be evaluated for the primary endpoints at 16-weeks.

Any participant consented, whether treated or not, will be assigned a screening number. The reason for failure to treat will be recorded in his/her study records and the site screening log.

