scores indicating a lower level of quality of life. The overall score and individual category scores will be used to demonstrate improvement over the course of the trial. Corresponding Skindex-29 cut-off scores for severely impaired HRQL are as follows: \geq 52 points on symptoms, \geq 39 on emotions, \geq 37 on functioning, and \geq 44 on the overall score. The estimated cut-off scores can be used in clinical practice to identify patients with (very) severely impaired HRQL

The Investigator will conduct a routine physical exam and record the following:

- i. Medical Assessment will be performed and the following information recorded:
- Complete history
- Physical Exam (including vital signs)
- Previous treatments for AGA
- Co-morbid conditions and any disabilities
- Duration and severity of AGA
- Concomitant medication usage
- Pregnancy Test urine dipstick (as required)
- ii. Assessments and Procedures will be collected as follows:
 - Hair Specific Skindex-29 Quality of Life Score Questionnaire

If a participant remains eligible, the Investigator will enter the participant into the study. Eligible participants will then have photographic assessments conducted and be trained on the components and use of REVIAN/SHAM and will undergo the first treatment at the PI's office. The day of the first treatment will be considered as the date of participant enrollment.

- Global Photography Image of Two Views (superior and vertex scalp)
- Shave and Tattoo Scalp
- Hair Count Macrophotography (1cm² Area)
- Instruction and 1st REVIAN/SHAM 10 Minute Treatment
- Adverse Events

A standard macrophotography technique will be provided to all investigational sites. Please refer to the Macrophotography Technique Manual for full instructions on the proper site selection for shaving and tattooing the scalp and macrophotography.

All participating investigators will undergo training on the appropriate use of the REVIAN/SHAM device. Only investigators and co-investigators qualified by training or experience in dermatological conditions of the scalp will be selected for this clinical trial.

All participants will be seen at 8-weeks, 16-, and 26-weeks following enrollment.

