- An **adverse event** (AE) is any untoward medical occurrence in a participant whether it is considered device related or not. Diseases, signs, symptoms, or laboratory abnormalities already existing at enrollment are not considered AE's unless they worsen (i.e., increase in intensity or frequency). Surgical procedures themselves are not adverse events; they are therapeutic measures for conditions that require surgery. The condition for which the surgery is required may be an adverse event. Surgical procedures planned prior to enrollment and the conditions leading to these measures are not adverse events.
- An adverse device effect (ADE) is any untoward and unintended response to a medical device, including events arising from insufficient or inadequate instructions for the employment of the device or its use.
- A Serious Adverse Event (SAE) is any AE that 1) results in death, 2) is lifethreatening, 3) results in or prolong hospitalization, 4) results in permanent impairment of a body function or permanent damage to a body structure, 5) necessitates medical or surgical intervention to preclude permanent impairment of a body function or permanent damage to a body structure.

Note: a device malfunction may or may not result in an AE. If a device malfunctions in a manner that causes an AE or a SAE as defined above, then the consequence of the malfunction will be reported as an AE or SAE, as appropriate. However, all device malfunctions will also be tabulated separately, regardless of whether or not an adverse event results from the malfunction.

Any SAE must be reported to the sponsor or designee by the Investigator within 24 hours of first learning about the event. A written report must be sent to the sponsor within ten working days of knowledge of the event to the fax number listed on the Serious Adverse Event Report Form.

The investigator is required to notify the IRB or EC in accordance with local reporting requirements.

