5.4 Safety Outcomes

Safety outcomes will be determined by evaluating by the type, frequency, severity, and relatedness of adverse events through the 26-weeks timepoint for all participants. All Adverse Events (AEs) will be tabulated and summarized as counts and percentages. AEs will also be cross-tabulated according to the following:

- Severity (Mild, Moderate, Severe)
- Seriousness (Serious, Non-serious)
- Device-Relatedness (Unrelated, Possibly Related, Probably Related, Definite)
- Procedure-Relatedness (Unrelated, Possibly Related, Probably Related, Definite)

In addition, the occurrence of any Unanticipated Adverse Device Effects (UADE) will be listed. The classification of severity, relatedness, and anticipated nature of AEs will be made by the investigator.

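### SAP 11.2 dates treatment-emergent events by report rather than onset, and its AE tables are narrower than protocol 5.4 requires, so harms of the baseline shave and tattoo can be left out

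*Combined protocol and SAP*

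**What the plan says.** **Order of Visit 2.** Protocol 3.4.2 lists global photography, "Shave and Tattoo Scalp", macrophotography, "Instruction and 1st REVIAN/SHAM 10 Minute Treatment" and, last, adverse events. The sentence above the list has participants photographed and then says they will "be trained on the components and use of REVIAN/SHAM and will undergo the first treatment at the PI's office".

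**Enrollment.** Protocol 3.4.2 says: "The day of the first treatment will be considered as the date of participant enrollment". Protocol 2.5 counts a participant as enrolled only once cap treatment has begun. Those who consent but "withdraw prior to the first treatment with REVIAN/SHAM will be considered a screening failure".

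**AE definition.** Under protocol 4.1, repeated in Appendix A, conditions "already existing at enrollment are not considered AE's unless they worsen".

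**Planned tabulation.** Protocol 5.4 requires all AEs to be tabulated as counts and percentages and crossed with severity, seriousness, device-relatedness and "Procedure-Relatedness (Unrelated, Possibly Related, Probably Related, Definite").

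**SAP.** Section 11.2 says "TEAEs will be defined as AEs reported after the first treamtment into the study". It summarizes these events by system organ class, preferred term, severity, relationship to treatment and seriousness. SAP section 6 makes the safety population the same as the ITT population, which is those who started treatment at baseline.

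**The concern.** A treatment-emergent event is normally one that begins or worsens on treatment. Defining it by report date lets an event's classification depend on when the participant happened to mention it. That matters here because the trial carries out its own procedure on the scalp, at the same visit and apparently before the first cap run.

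The protocol recognizes that this procedure can cause harm. It excludes people with known sensitivity or allergy to tattoo ink, and it asks for the relation of each AE to the procedure. The type, frequency, severity and relatedness of AEs are the primary safety outcome (protocol 5.1, SAP section 8). If the SAP tables are built as written, the reader of the study report may see no count of harms from the baseline shave and tattoo. Some events that began before the cap was worn could also appear as emerging on it.

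**Working it through.** No arithmetic applies to the definitions. The check sets them side by side and follows each kind of event through.

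**Does the procedure precede the cap?** The list and the prose in protocol 3.4.2 both place photography before the first treatment, and macrophotography images the shaved and tattooed site. The schedule table in protocol 3.4.8 has the first-application row above the shave-and-tattoo row, but it shows only that both belong to Visit 2. The better reading is that the procedure comes first.

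**When does enrollment occur?** Protocol 2.5 ties it to beginning treatment, which is a moment. Protocol 3.4.2 ties it to a calendar day, which also contains the shave and tattoo. The AE definition uses enrollment as its cut-off, so the two readings give different answers for a same-day reaction.

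**What happens to each event?**

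| Event | AE under protocol 4.1? | Treatment-emergent under SAP 11.2? | In a SAP AE table? |
|---|---|---|---|
| Reaction to shave or tattoo, reported before the cap run, gone by then | Yes | No | No |
| Reaction still present and unchanged at the cap run | No if enrollment is the moment of starting; arguably yes if it is the day | Only if it is an AE and is reported after the cap run | Depends on both |
| Event after consent that cleared before the cap run, first mentioned at the Week 1 call | Yes | Yes | Yes, although it began before treatment |
| Reaction in someone who leaves before the cap run | Not addressed, since there is no enrollment | No | No: screening failure, outside the safety population |
| Reaction that begins after the cap run, or after re-inking at week 8, 16 or 26 | Yes | Yes | Yes |

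The first, third and fourth rows do not depend on how enrollment is read.

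**Do the SAP outputs meet protocol 5.4?** Tables 14.3.1.1 to 14.3.1.6 are the only AE tables, and all six are titled for treatment-emergent events in the safety population. Table 14.3.1.4 is by relatedness without saying to what; the text of 11.2 names relationship to treatment and does not mention the procedure. The list of listings contains one entry, for major protocol deviations. No planned AE table covers all AEs, and none is specified by procedure-relatedness.

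**Is an onset rule feasible?** Yes. Protocol 4.1 already records onset and resolution dates, and SAP 9.4 and 11.1 already classify medications by when they start and stop relative to treatment.

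**The case against.** The best case for the plan is that it clearly means to capture these harms, and much of the apparent loss is closed elsewhere.

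- **Visit order.** Adverse events come after the first cap run in the Visit 2 list. A reaction elicited at that point is reported after first treatment and, if it is an AE, it is treatment-emergent. The report-date rule loses only a reaction formally reported in the short gap before the cap run. This stands, and it makes the loss smaller.
- **Calendar-day enrollment.** A Day 0 reaction need not count as pre-existing. A reader might infer that any reaction beginning before the cap run falls outside the AE definition. The documents do not support that: protocol 3.4.2 defines enrollment by the day, and the pre-existing clause reads naturally as meaning background conditions. What stands is an ambiguity, because protocol 2.5 points the other way.
- **No double counting.** A reader might also infer that an unchanged reaction is both excluded as pre-existing and later counted as treatment-emergent. It cannot be both, since only AEs can be treatment-emergent. Misclassification by late reporting concerns events that cleared before the cap run. An event that later worsens arguably belongs in the tables.
- **Other records.** AEs are collected at baseline with their relation to the procedure. SAP section 8 promises listings of all outcomes. Protocol 2.5 requires the reason for not treating to be logged, and protocol 5.8 says available information on people screened but not enrolled will be summarized. The data are therefore not simply lost. None of this is the tabulation that protocol 5.4 requires, and no structured AE summary is guaranteed for someone who was tattooed but never treated.

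**Conclusion.** The point holds in two parts. SAP 11.2 uses report date where onset is available, and its AE tables are narrower than protocol 5.4: treatment-emergent events only, treated participants only, and no stated procedure-relatedness. Harms of the baseline shave and tattoo can therefore be left out of the AE tables, and some events with earlier onset can be counted as treatment-emergent. The wording for same-day reactions in the AE definition is ambiguous rather than plainly wrong.

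The size is unknown, because the documents give no rate of shave or tattoo reactions. Under an assumed rate of immediate reactions of 1% to 5% in 200 participants, 200 × 0.01 = 2 and 200 × 0.05 = 10 people would have one. This is a ceiling under that assumption and not an estimate of events lost, since many such reactions would be recorded after the cap run or persist into follow-up.

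A reader might infer that the safety comparison of active caps with sham is biased. The documents do not support that, because the baseline procedure is the same in every arm. What is affected is the absolute count of procedure harms and the attribution of events to the cap. The conclusion rests on the procedure preceding the cap run, as protocol 3.4.2 has it. The mismatch between protocol 5.4 and the SAP tables does not depend on that order.

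**What to change.** 1. **SAP 11.2:** define a treatment-emergent event as an AE with onset, or worsening, at or after the start of the first cap run.
2. **SAP tables:** add the tabulation of all AEs by procedure-relatedness that protocol 5.4 requires, and state in table 14.3.1.4 what the relatedness refers to.
3. **SAP listings:** add one listing of AEs with onset from the first study procedure to the first cap run, with relation to the procedure. Include participants who had the shave and tattoo but were never treated.
4. **Protocol 4.1 and Appendix A:** state that a reaction to the study's own shave or tattoo is not a pre-existing condition, and align the enrollment wording in 2.5 and 3.4.2 for this purpose.

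The cost is one table, one listing and a few sentences. Onset date is already on the AE form; Visit 2 events would also need an onset time. The count of mild procedure events would rise slightly. No visit or assessment is added.
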